Clinical Investigation Plan

CP343

A randomized, controlled clinical investigation of an improved two-piece stoma product for people living with a stoma

Version 2.0, 14 October 2022

NCT05652010

This confidential document is the property of Coloplast A/S. No unpublished information contained herein may be disclosed without written approval of Coloplast A/S.

CHANGE LOG

VERSION NUMBER	ISSUED BY (INITIALS)	COMMENTS (MAJOR CHANGES SINCE LAST REVISION)
[REDACTED]	[REDACTED]	[REDACTED]

SYNOPSIS OF THE CLINICAL INVESTIGATION

Title

CP343: A randomized, controlled clinical investigation of an improved two-piece stoma product for people living with a stoma

Test Product and Comparator:

Test Product:

- SenSura Mio Click maxi bag (open, wide outlet), 50mm Ø with new coupling and lock ring
- Baseplate flat: SenSura Mio, click base plate with belt ears, 50 mm, 10-45 mm [REDACTED]
- Baseplate Concave: [REDACTED] SenSura Mio Concave, click base plate with ears size Ø50, 10-45 mm

Comparator:

- SenSura Mio Click 2p bag [REDACTED] Open, wide outlet, maxi, neutral grey. 50mm [REDACTED]
- Baseplate flat: [REDACTED] SenSura Mio Click Base Plate with belt ears, 50 mm, 10-45 mm
- Baseplate concave: [REDACTED] SenSura Mio Concave, click base plate with ears size Ø50, 10-45 mm

Objective(s)

The objective of the study is to investigate how a new two-piece (2p) coupling system performs in comparison with SenSura Mio Click regarding leakage at the coupling during wear (at each bag change) in a clinical setting.

[figure not shown]
Design of the investigation

Open-label, randomized, controlled, comparative, cross-over study with 2 test sequences comparing a new 2p coupling system with SenSura Mio Click. Each test period is 3 weeks (\pm 2 days), total study period is 6 weeks (\pm 4 days). It will be a 1:1 randomization into the two possible treatment sequences.

The investigation will require 50 randomized subjects (exp. 20% drop-out), leading to at least 40 completed subjects. The sample size calculation is based on at least 6 bag changes during each test period (\geq 2 changes per week).

All visits will be performed as remote virtual calls. At the visits, the investigator (or designee) will give instructions for the coming period and check that the trial is running as planned. At every bag change the subject will be asked to complete a questionnaire.

Cross-over design with two sequences

A follow-up call will be scheduled 7 ± 1 days after each test visit to ensure compliance with the provided product and study procedures. Additional calls may be scheduled if needed (assessed by the Principal Investigator or designee).

A subject is considered enrolled once consented. Screen failures are considered subjects who have consented, yet do not meet eligibility based on inclusion and/or exclusion criteria or withdraw consent prior to being randomized.

A subject can be randomized by mistake e.g., if the investigator realizes that the subject is not eligible after the subject has been randomized. If the subject has not started study treatment and has no data registered on endpoints the subject can be replaced by a new subject if the new subject can complete the investigation within timelines (before last subject last visit and within visit windows). A screen failure will be replaced under the same conditions.

Expected duration of the clinical investigation:

The investigation will be conducted from December 2022 through June 2023.

Endpoints & Assessments:

Primary Endpoint:

- Leakage through coupling registered at each bag change (yes/no).

Secondary endpoints:

- Product satisfaction evaluated at end of study by a question on a 4-point scale
- Preference evaluated at end of study by the question "Would you consider using the new coupling in the future? (Yes/No)"

Exploratory endpoint

Assessments

- Level of leakage at each bag change. If the subject responds as "yes"; the subject will be asked to grade the leakage on a 3-point scale.

Safety assessments:

- Adverse events
- Device deficiencies

Registered at the inclusion visit by Investigator or designee:

- Informed Consent
- Subject number
- Date of visit
- Check of inclusion criteria
- Check of exclusion criteria
- Current product (flat / concave, current bag size), item numbers (bag and baseplate)
- Name/type of randomized product

Baseline information and questions (registered at the inclusion visit by investigator or designee):

- Demographic (age, gender, height, weight)
- Stoma (age, type, cause, size, shape)
- For colostomy: Bristol stool scale
- Output frequency

Population/subjects

Subjects with an ileostomy or subjects with a colostomy with liquid fecal output, currently using the SenSura Mio Click 2p coupling (50mm Ø) with a flat or concave baseplate. The investigation will require 50 randomized subjects (expected 20% drop-out), leading to at least 40 completed subjects. Subjects will be enrolled through a single center

Definition of liquid fecal output for subjects with a colostomy: Six or seven on the Bristol stool scale (Appendix 1)

Inclusion/Exclusion Criteria:

To be included in the investigation a subject must comply with the following inclusion criteria:

1. Has given written consent to participate by signing the Informed Consent Signature Form
2. Be at least 18 years of age and have full legal capacity
3. Is able to handle (apply, remove, cut, etc.) the product and do the assessments themselves
4. Has an ileostomy or colostomy with consistent liquid fecal output (for colostomy: 6-7 Bristol stool scale*)
5. Currently use SenSura Mio Click 2p Click flat or concave with 50 mm coupling size
6. Have had their ostomy for at least 90 days
7. Be willing to change the bag at least twice per week
8. Is willing and suitable (determined by the Principal Investigator or designee) to use flat or concave 2p open product during the investigation
9. Is willing to use 2p maxi open bags during the investigation

A subject is excluded from the investigation in case he/she:

1. Is currently receiving or have within the past 60 days received radio-and/or chemotherapy
 - low doses radio- and/or chemotherapy (assessed by Principal Investigator) is allowed for indications other than cancer.

2. Is currently receiving or have within the past 30 days received topical steroid treatment in the peristomal skin area, e.g., lotion or spray

- Low dose systemic steroid treatment (e.g., inhalation) assessed by the investigator are allowed.- Other systemic steroid treatment (e.g., injection or tablet) are not allowed.
3. Is pregnant and/or breast-feeding
4. Have a loop ileostomy
5. Is currently using convex baseplate
6. Has known hypersensitivity towards any of the products used in the investigation

LIST OF ABBREVIATIONS

ABBREVIATION	WRITTEN OUT	EXPLANATION (IF APPLICABLE)
ADE	Adverse Device Effect	See section 18.1
AE	Adverse Event	See section 18.0
ASADE	Anticipated Serious Adverse Device Effect	See section 18.5
CIP	Clinical Investigation Plan	

1.1. Site Personnel

This clinical investigation will be conducted in the United States at a single-center [REDACTED].

The Clinical Manager is responsible for maintaining an updated list of all sites and personnel in the sponsor electronic trial master file (eTMF). Qualified site personnel can perform investigational related tasks per the Principal Investigator's (PI) delegation. This delegation must be documented in the 'Site Personal Signature and Delegation List' for each site. All PIs and designees will receive training in all aspects of the investigation and before they can begin any study related procedures.

1.2. Clinical Research Organizations

A Site Management Organization (SMO) will be used to help conduct the investigation as a clinical site. All sponsor representatives' roles and responsibilities will be listed on the 'Site Personnel and Contact Details List'.

1.3. Other Vendors

The data management system is delivered by [REDACTED]. The system is designed for electronic data capture, and it is compliant with the requirements of 21 CFR part 11.

The subject will be required to download and install a Patient Cloud app onto their smart phone. See section 11 for further details.

The app will be used to record subject diary responses.

In case of emergency, please contact the Clinical Manager from the above list of sponsor representatives.

2. Justification for conducting the clinical investigation

People with intestinal stomas have, despite development of better stoma products, problems with leakage induced peristomal skin complications which influence quality of life negatively^{1,2}. Although, the primary cause of peristomal skin complications is leakage of ostomy effluents under the adhesive barrier^{3,4}, leakage could also occur from other parts of stoma devices, for example through the coupling in 2-piece stoma devices. Coloplast wants to apply a new coupling system with improved functionality for SenSura Mio users who use a 2-piece appliance. The justification for conducting this clinical investigation is to investigate that the new coupling system is on par with the existing coupling SenSura Mio Click system with regards to leakage at the coupling.

3. Objective(s) of the clinical investigation

The aim of the study is to investigate how a new two-piece (2p) coupling system is evaluated by users in comparison with SenSura Mio Click.

The primary objective is to demonstrate that the performance of the new 2p coupling system is comparable to SenSura Mio Click coupling with regards to leakage at the coupling during wear in a clinical setting.

The secondary objective is to evaluate product satisfaction and preference of the new two-piece (2p) coupling system by users in a clinical setting.

4. Investigational Products

4.0. Description of Test Product

The test product consists of the following:

- SenSura Mio Click maxi bag (open, wide outlet), 50mm Ø [REDACTED] with a new coupling and lock ring
- Baseplate flat: SenSura Mio, click base plate with belt ears, 50 mm, 10-45 mm [REDACTED]

- Baseplate concave: [REDACTED] SenSura Mio Concave, click base plate with ears size Ø50, 10-45 mm

4.1. Description of the comparator product(s)

The following comparator products will be used in this investigation:

- SenSura Mio Click 2p bag [REDACTED]. Open, wide outlet, maxi, neutral grey. 50mm [REDACTED]
- Baseplate flat: [REDACTED] SenSura Mio Click Base Plate with belt ears, 50 mm, 10-45 mm
- Baseplate concave: [REDACTED] SenSura Mio Concave, click base plate with ears size Ø50, 10-45mm

The comparator products are already on the market and will be used within the intended purpose in this clinical investigation.

4.2. Manufacturing

The Test Products and comparators will be manufactured at Coloplast A/S, [name].

4.3. Identification and traceability of the device

All investigational products (test and comparator products) are labelled as per regulations and include "CAUTION – Investigational device. Limited by United States law to investigational use" on the label. The products are also identified with study number, product name/code, and item/lot number and accounted for through a master sponsor accountability log. Upon IRB approval, investigational products will be shipped to the principal investigator, or designee. Additionally, all investigational products will be accounted for and documented on a site accountability log. The receipt and disposition of all investigational products will be verified through monitoring. All unused products will be returned to Coloplast at the end of the study.

4.4. Intended use of the device in the clinical investigation

The test product is intended to support collection of output from a stoma and to provide a seal between the bag and baseplate.

4.5. Intended population for the device

The test product is indicated for use with surgically created ileostomies and colostomies with liquid fecal output. The product is indicated for adults currently using SenSura Mio Click 2p coupling (50mm Ø) open bags with flat or concave baseplate. Definition of liquid fecal output for subjects with a colostomy (6-7 on the Bristol stool scale - See Appendix 1)

4.6. Handling of the investigational device

The handling of the investigational products is described in detail in the Instruction for Use (IFU), which is included in all boxes with the products.

All site personnel will receive training by the sponsor and/or principal investigator in the handling and correct use of the investigational products. The Principal Investigator, or designee, will train the subjects in the correct use of the investigational products.

For further details regarding the test product, please refer to the Investigators Brochure.

4.7. Total number of devices intended for the clinical investigation

The subjects will be included for $21^{+/-2}$ days per test period, for approximately 42 days.

Subjects are expected to change their products at least twice a week, but may change more frequently, and as frequently as once a day. Therefore, it is estimated subjects may use approximately 21 test product baseplates and 21 comparator baseplates during their participation. Subjects will be supplied with enough baseplates and bags for the duration of the investigation.

5. Design of the clinical investigation

5.0. General

This investigation is an open-label, randomized, controlled, comparative, cross-over study with 2 test periods and 2 test sequences comparing a new 2p coupling system with SenSura Mio Click. Each test period is 21 days (± 2 days). Each subject will participate for a total of 42 days (± 4 days). The subjects will test the investigational product and the comparator in a 1:1 randomised order. A total of 50 subjects will be enrolled and

randomized to yield 40 subjects (assuming a 20% drop-out rate) who complete the study. The sample size calculation is based on at least 6 bag changes during each test period (≥ 2 changes per week).

If a potential subject is interested in participating after the first contact, a visit (visit 0) will be arranged.

The subject will receive both written and verbal information to ensure that the subject understands what was read and explained and can freely agree to participate in the investigation. During the visit, the Principal Investigator or designee will provide oral information about the investigation based on the Subject Information Form.

Before the test periods, the subjects are invited for a screening visit (V1). Subjects will be consented prior to any study procedures. Once consented, during their participation, the subjects will complete three study visits (V2, V3 and V4). The visits will be done remotely via video conference. A follow-up call will be scheduled 7 \pm 3 days after each test visit to ensure compliance with the provided product and study procedures. Additional calls may be scheduled if needed (assessed by the Principal Investigator or designee).

At every bag change the subject will be asked to complete a questionnaire via an app installed on their smartphone.

During the visits the subject will complete a questionnaire and discuss any adverse events or device deficiencies they may have had with the site personnel.

Coloplast will provide both the investigational product and the comparator product for all subjects.

If a subject experience a problem with the investigational product during the investigation, he/she should contact the investigator for advice. Subjects that cannot complete a test period with the test product may choose to use their own product (i.e., SenSura® Mio) for the remainder of the test period. However, this must be documented by the Principal Investigator.

[figure not shown]

Figure 1 Design of the investigation.

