5.9. Blinding

No blinding will be used in this investigation, as it is not possible to blind the products due to visible differences. The trial statistician will be blinded until database lock to ensure decisions related to data before database lock do not affect the final results.

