6.1. Inclusion criteria

To be included in the investigation a subject must comply with the following inclusion criteria:
1. Has given written consent to participate by signing the Informed Consent Signature Form
2. Be at least 18 years of age and have full legal capacity
3. Is able to handle (apply, remove, cut, etc.) the product and do the assessments themselves
4. Has an ileostomy or colostomy with consistent liquid fecal output (for colostomy: 6-7 Bristol stool scale*)
*See appendix 1
5. Currently use SenSura Mio Click 2p Click flat or concave with 50 mm coupling size
6. Have had their ostomy for at least 90 days
7. Be willing to change the bag at least twice per week
8. Is willing and suitable (determined by the Principal Investigator or designee) to use flat or concave 2p open product during the investigation
9. Is willing to use 2p maxi open bags during the investigation

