6.5 Subject Screening and randomization Failures

Subjects that have signed the informed consent form but fail to comply with the eligibility criteria are considered screening failures. A screening failure will be replaced by a new subject if the new subject can complete the investigation within timelines (before last subject last visit and within visit windows).

Screen failures are also considered subjects who have consented but withdraw consent prior to being randomized.

In rare cases, randomization errors can occur, and subjects are randomized by mistake, e.g., if the investigator realizes that the subject is not eligible after the subject has been randomized. In these cases, if the subject has not started study treatment and has no data registered on endpoints; the subject can be replaced by a new subject if the new subject can complete the investigation within timelines (before last subject last visit and within visit windows).

If a subject is randomized to one test sequence but by mistake gets products for the opposite sequence it will be regarded as a randomization failure. As this is an exploratory investigation the statistical analyses will in that case be based on the actual test sequence and not the randomized sequence

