 - Investigator/study nurse must call the subject to ensure that the subject is compliant with:
 - Study procedures and
 - Completion of subject diary
- Diary completion at every bag change
- Adverse Events, if applicable
- Device Deficiencies, if applicable
- Protocol Deviations, if applicable

Visit 3 - Cross-over Visit (Day 25 ± 2 days)

- Subject will be contacted by investigator/study nurse to review procedure for cross-over
- Study Personnel will review compliance with subject and collect safety data, if applicable. Application of investigational product - test product OR comparator (Day 1 of Test period 2)
- Adverse Events, if applicable
- Device Deficiencies, if applicable
- Protocol Deviations, if applicable

Test period 2:

- Testing test product / comparator product for 21 ± 2 days
- Telephone Visit at Day 7 ± 1 after application of product/comparator:
 - Investigator/study nurse must call the subject to ensure that the subject is compliant with:
 - Study procedures and
 - Completion of subject diary
- Diary completion at every bag change
- Adverse Events, if applicable
- Device Deficiencies, if applicable
- Protocol Deviations, if applicable

Visit 4 – Completion/Termination (Day 46 ± 2 days)

- Subject will be contacted by investigator/study nurse for study completion or termination
- Study Personnel will review compliance with subject and collect safety data, if applicable.

NOTE:

1. See Appendix 2 for details on the subject questions included in the subject diary. The subject diary will be provided to the subjects using an app installed on their smart phones.
2. Subjects who are unable to complete a test period may move forward to the next visit and test period instead of dropping out of the investigation.

7.2. Safety Follow up:

Adverse events and device deficiencies will be assessed at all visits, planned and unplanned. Subjects are followed through termination of the investigation (Visit 4). Any ongoing ADEs or SADEs at study termination will be followed until resolution. All subjects are encouraged to contact the Principal Investigator, or designee, if they experience problems that they believe are related to their investigational product or participation. This is to ensure that any device-related events are documented and to safeguard the subjects' health.

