10.0. Statistical design, method, and analytical procedures

The primary objective will be evaluated by analysis of the primary endpoint [REDACTED]

[REDACTED]. The secondary objective will be evaluated by analysis of the secondary endpoints.

All baseline measurements, endpoints and assessments will be summarized by descriptive statistics and/or listed. Endpoints and assessments will be summarized by product. Descriptive statistics for continuous variables are presented with N, Mean, SD (standard deviation), Median, Min and Max, where N denotes the number of subjects contributing with non-missing data. For discrete variables, descriptive statistics are presented with N and percentage, where percentage is based on the total number of subjects/observations with non-missing data.

Other summaries can be made, if relevant. As it is an exploratory study no adjustment for multiple testing will be applied.

All statistical analysis and summaries will be performed with SAS (version 9.4/Enterprise Guide version 7.1)

Definition of analysis populations

Intention to Treat (ITT) and Safety populations will be defined at a formal data review meeting before database lock. As a minimum, the data manager, the clinical manager, and the statistician will be involved in the classification of subjects.

The ITT population (full analysis set) will be constituted by all included subjects with valid informed consent who have been exposed to at least one product, with information on at least one product with respect to the primary endpoint or the secondary endpoints.

Any exclusion of subjects from the ITT population must be documented. Invalid individual data points may be omitted from analysis even though the corresponding subject is part of the ITT population. Any exclusion of data points will be documented.

The Safety population will be constituted by subjects who have given informed consent.

All statistical analysis will be based upon the ITT population whereas adverse events and device deficiencies will be assessed based on the safety population.

Considering the data obtained it might be considered to make additional explorative analyses based on a subset of the ITT population.

Analysis of the primary endpoint

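### Does letting subjects return to their own SenSura Mio during the test-product period leave the leakage comparison undefined?

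*Combined protocol and SAP*

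**What the plan says.** Section 5.0 sets the fallback: "Subjects that cannot complete a test period with the test product may choose to use their own product", which it identifies as SenSura Mio, until the period ends. It adds: "However, this must be documented by the Principal Investigator". Inclusion criterion 5 in Section 6.1 fixes what that product is: "Currently use SenSura Mio Click 2p Click flat or concave with 50 mm coupling size". This is the comparator's coupling system. Section 7.1 (note 2) gives another way out: "Subjects who are unable to complete a test period may move forward to the next visit and test period".

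The primary model in Section 10.0 is a logistic mixed model. Its product factor has the levels SenSura Mio and test product, with a period effect, a random subject effect and a random product-by-subject effect. It estimates a marginal leakage proportion per product. Section 10.0 also plans descriptive tables: "Endpoints and assessments will be summarized by product", where "percentage is based on the total number of subjects/observations with non-missing data".

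The only explicit rule on actual against assigned product is in Section 6.5, for subjects supplied in the wrong sequence: "the statistical analyses will in that case be based on the actual test sequence and not the randomized sequence".

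Section 10.3 counts the purpose as fulfilled if the leakage proportions do not differ significantly, or if the estimated difference is not worse to a clinically relevant degree.

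**The concern.** A subject who reverts keeps filling in the diary at every bag change. The test-product period can therefore hold primary-endpoint records that describe the comparator coupling. No visible sentence assigns those records to a product. The questionnaire in Appendix 2 does not ask which product was worn, and a programmer working from the randomisation list could derive product from sequence and period.

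The likely error has a direction. If leakage prompts reversion, coding by assigned period dilutes the test arm with comparator records. Even with records coded as worn, the crude percentages lose leak-prone subjects from the test rows early and gain them in the SenSura Mio rows. The test percentage falls, the SenSura Mio percentage rises, and the difference between them shrinks. Under Section 10.3 both a non-significant result and a small difference count as success, so a truly worse coupling would pass more easily.

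**Working it through.** **1. The plan's own figure.** Section 6 needs 40 completers and assumes 20% drop-out: 40 / (1 − 0.20) = 50, as stated. The 40 cannot be rebuilt because the rates, effect and power in Section 10.1 are redacted. Leakage rates, reversion rates and random-effect SDs below are therefore assumptions.

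**2. What the text supports.**

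| Coding of own-product changes | Support in the visible text |
|---|---|
| As worn (SenSura Mio) | 5.0 names the fallback SenSura Mio; that is a level of the product factor in 10.0; tables are by product; 6.5 follows actual use |
| Excluded | 10.0 allows invalid data points to be omitted, with documentation |
| By assigned period (test product) | Only the ITT label, but 10.0 defines that set by exposure and endpoint data, not by assignment |

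On the second gap, 10.3 speaks of an estimated proportion and an estimated difference. In 10.0 it is the model's proportions that are estimated, while the percentages are described as summaries.

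**3. Size of the coding choice.** Model: logit P(leak) = intercept + product + period + subject + subject × product. Inputs: 40 subjects, 20 per sequence, both SDs 1, reversion after the second recorded test-product leak, own product leaking at the subject's comparator rate, 1,000 trials per scenario, likelihood-ratio test at 5%. Differences are in percentage points (Monte Carlo SE of the model differences 0.05 to 0.11).

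| Scenario | Model, no reversion | Model, as worn | Model, excluded | Model, by period | Crude %, no reversion | Crude %, as worn |
|---|---|---|---|---|---|---|
| 5% v 10%, 6 changes | 4.98 | 5.07 | 5.05 | 4.06 | 5.00 | 3.55 |
| 5% v 15%, 6 changes | 9.96 | 10.04 | 10.02 | 7.71 | 9.99 | 7.49 |
| 5% v 10%, 12 changes | 4.86 | 4.91 | 4.89 | 2.92 | 4.89 | 1.97 |
| 5% v 15%, 6 changes, half revert | 9.96 | 10.00 | 9.99 | 8.89 | 9.99 | 8.78 |

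The probability of a non-significant result, in row order, is 54.3, 9.9, 41.0 and 10.3% as worn; 54.5, 10.2, 41.5 and 10.4% with exclusion; and 61.4, 14.9, 57.5 and 12.5% by period. The two codings that the text supports agree within 0.5 points. Only by-period coding departs, by 7.1, 5.0, 16.5 and 2.2 points from as worn.

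**4. A harsher setting.** With 5% v 10%, 7 changes, SDs 1.5 and 0.7, reversion after the first leak and 300 trials, the model gives 5.1 points without reversion, 5.3 as worn, 5.3 with exclusion and 2.6 by period. Non-significance is 43, 53, 54 and 77% (Monte Carlo error about 3 points). The rise from 43 to 53% is lost information, not bias, and neither supported coding recovers it. With equal true rates of 10%, the crude difference is −5.1 points and the model, as worn, shows 0.2.

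**5. Why the crude difference shrinks.** In a rerun of the first scenario, the crude difference is 5.0 without reversion, 3.9 with own-product rows removed and 3.6 with them counted as SenSura Mio. Of the 1.4 points lost, 5.0 − 3.9 = 1.1 come from leak-prone subjects leaving the test rows early and 3.9 − 3.6 = 0.3 from the added SenSura Mio rows. Subjects who move on under Section 7.1 would cause nearly the same loss, so a coding rule barely alters the percentages.

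**6. Dependence on assumptions.** In the first scenario the crude difference falls by 1 − 3.55/5.00 = 29%. The fall is about 13% if half of the triggered subjects revert, 7% if a quarter do, 11% if a third leak is the trigger, and 6 to 7% with both SDs at 0.5. It is nil if reversion is unrelated to leakage.

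**The case for a change.** The best case for a change is that the rule costs one sentence, the trial is open-label, the error would run towards passing, and by-period coding is an easy default when the diary does not ask which product is on. One could add that an analysis labelled ITT might keep the assigned product after a switch. An own bag also need not be the study's comparator bag, since criterion 5 fixes the coupling and not the bag.

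Some of this stands. Neither the coding rule nor the source of the difference in 10.3 is written in the visible text, and a reader of the descriptive tables could be misled if many leak-prone subjects stop early.

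The rest does not lead to a different plan. The objective is how a coupling performs in wear, so labelling a bag change with a coupling that was not on the subject would contradict the factor's own levels. Whether an own bag is pooled with the comparator or set aside hardly matters, because both give the same model result. The switch can be located: the investigator documents it, the accountability log in Section 14 holds dates of use, and diary entries carry date and time. Data points are settled at a review before lock, and "The trial statistician will be blinded until database lock". A rule could also sit in the redacted parts of Sections 10.0 and 10.1.

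**Conclusion.** No change is needed. This is a gap that analysts fill sensibly from the text as it stands. With own-product changes coded as worn or excluded, the planned model returns the difference seen without reversion to within about 0.1 point in the four main scenarios and about 0.2 point in the harsher one. The damaging results need either by-period coding or a decision taken from crude percentages, and the visible text supports neither. Writing the rule down would record what is already implied and would leave the design, the model and the fallback as they are.

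The conclusion rests on assumed leakage and reversion rates, and on reversion depending only on leaks recorded in the diary. The simulated data were analysed with the model that generated them, so recovery by that model is expected and is not independent proof. If subjects revert for unrecorded reasons tied to leakage, no coding rule corrects it. The absence of a numerical margin in Section 10.3 is a separate matter and is not judged here.
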